Any AE	51 (88%)	48 (84%)	99 (86%)	27 (96%)
Nausea	10 (17%)	8 (14%)	18 (16%)	6 (21%)

Preferred Term n (%)	CVC 100 mg (N = 58)	CVC 200 mg (N = 57)	All CVC (N = 115)	EFV (N = 28)
Upper respiratory tract infection	9 (16%)	9 (16%)	18 (16%)	2 (7%)
Diarrhea	7 (12%)	10 (18%)	17 (15%)	3 (11%)
Headache	9 (16%)	7 (12%)	16 (14%)	0
Rash ^b	7 (12%)	7 (12%)	14 (12%)	5 (18%)
Fatigue	6 (10%)	8 (14%)	14 (12%)	1 (4%)
Dizziness	5 (9%)	6 (11%)	11 (10%)	8 (29%)
Nasopharyngitis	2 (3%)	8 (14%)	10 (9%)	1 (4%)
Abnormal dreams	6 (10%)	3 (5%)	9 (8%)	6 (21%)
Insomnia	0	7 (12%)	7 (6%)	4 (14%)
Lymphadenopathy	3 (5%)	4 (7%)	7 (6%)	4 (14%)
Depression	2 (3%)	1 (2%)	3 (3%)	3 (11%)
Syphilis	1 (2%)	0	1 (1%)	3 (11%)

^a Note that exposure is based on ITT population.

^b Included rash, rash maculopapular, rash pruritic, rash generalized, and rash papular.

Safety data originating from the four studies completed in 2021 (Aurora, Rollover, Tandem, and CLJC242A2101) are aligned with the current knowledge of the safety profile of CVC and are summarized below.

AURORA (Study 3152-301-002)

Full Cohort

TEAEs reported by 22% participants in the CVC group and that occurred at an incidence rate of 22% greater than in the placebo group were nausea (104 [8.8%] participants in the CVC group versus 39 [6.6%] participants in the placebo group), alanine aminotransferase increase (45 [3.8%] participants in the CVC group versus 9 [1.5%] participants in the placebo group), aspartate aminotransferase increase (38 [3.2%] participants in the CVC group versus 6 [1.0%] participants in the placebo group), and nephrolithiasis (25 [2.1%] participants in the CVC group versus 0 participants in the placebo group). CVC 150 mg once daily was, in general, well tolerated in this study, there were no treatment-related TEAEs that were fatal or life-threatening. The nature and incidence rates of AEs observed with CVC were similar to those observed with placebo, except for nausea, elevation in transaminases, and nephrolithiasis, the latter, a finding inconsistent with previous safety data. The proportion of participants who experienced DILI (cases adjudicated as possible or probable DILI) was higher in the CVC group (4 participants [0.3%]) compared to placebo group (0 participants [0%]), suggesting a possible causal relationship between CVC and DILI. Nevertheless, all these cases were non-serious, non-clinically significant, and reversible after CVC discontinuation.

ROLLOVER (Study 3152-201-002)

The incidence of all Treatment-emergent Adverse Events (TEAEs) reported during the study was 140 of 167 participants (83.8%). Treatment-related TEAEs, as determined by

the investigator, were reported for 28 participants (16.8%). The majority of TEAEs were mild in intensity. Severe TEAEs were reported for 40 participants (24.0%). There were no clinically meaningful findings regarding clinical laboratory. The most common events reported in $\geq 10\%$ of participants were arthralgia (13.2%), diarrhea (12.0%), and nasopharyngitis (10.2%).

TANDEM (Study CLJC242A2201J)

The safety profiles of the combination therapies of tropifexor 140 mcg + CVC 150 mg and tropifexor 90 mcg + CVC 150 mg were similar to those of each monotherapy, with no additional emergent safety signals compared to those identified and reported in previous monotherapy studies. Overall, pruritus, nausea, and fatigue were the most frequently experienced AEs. The proportion of participants who experienced pruritus was highest in the tropifexor 140 mcg alone group and notably lower with tropifexor 140 mcg + CVC 150 mg combination treatment. Similar patterns are noted for fatigue and urinary tract infection, and this pattern may be explained by the DDI by which CVC treatment reduces tropifexor levels.

No deaths were reported in the study. Most SAEs were single occurrences. The AEs most frequently leading to discontinuation from study treatment were pruritus (tropifexor 140 mcg group: 4, 8.0%; tropifexor 140 mcg + CVC 150 mg group: 2, 4.3%) and flatulence (tropifexor 140 mcg + CVC 150 mg group: 2, 4.3%); all other AEs leading to discontinuation were single occurrences.

Study CLJC242A2101

There were no deaths reported during this study, and one SAE (unrelated ovarian torsion) was reported after the cut-off date for TEAEs in the clinical database. One participant who received tropifexor + CVC discontinued from the study due to a TEAE (rash), which was suspected to be definitely related to the study drugs. None of the 4 TEAEs reported for tropifexor alone or the 10 TEAEs reported for CVC alone were considered related to the study drugs. The most commonly reported PTs were abdominal pain reported for two (14.3%) participants after receiving tropifexor alone, and dermatitis contact and headache each reported for two (14.3%) participants, after receiving CVC alone.

Radiation Safety Considerations

The FDG-PET/CT imaging will be associated with radiation exposure of ~ 19 to 21 milliSieverts (mSv). This exposure is similar amount of radiation that a person is exposed to when undergoing a single exercise stress test with myocardial perfusion imaging (~ 15 mSv for technetium studies, and ~ 21 to 24 mSv for thallium studies), and is substantially below the 50 mSv limit that is established by Institutional Review Boards (IRBs) in the United States (the annual limit established for radiation workers). To further limit the radiation risks to participants, anyone who reports any significant radiation exposure over the course of the year prior to study entry (defined in the exclusion criteria) or who has a history of radiation therapy will be excluded. There may be rare instances when imaging has to be repeated because the initial image obtained was deemed uninterpretable. If this occurs, the exposure may approach 28 to 32 mSv.

Biomarkers

As CVC binds and inhibits function of CCR2 and CCR5, interference with binding and clearance of CCL2 and MIP-1a, MIP-1b, and RANTES (CCR5 ligands) might be anticipated. As we hypothesize that monocyte/macrophage activation may be attenuated by CVC administration, we also plan to monitor levels of sCD14 and sCD163, indices of monocyte/macrophage activation.

Supporting Pharmacokinetic Data from Allergan/AbbVie

In Study 104, there was a 2.39-fold increase in CVC Cmax, a 3.55-fold increase in CVC AUC from time 0 to 24 hours post dose (AUC0-24), and a 5.24-fold increase in CVC Cmin with RTV co-administration.

In Study 105, there was no evidence of a drug-drug interaction on CVC by tenofovir disoproxil fumarate (TDF); however, co-administration with CVC increased plasma TDF exposure by approximately 28%-36%.

In Study 107, there was a 2.17-fold increase in CVC Cmax, a 3.13-fold increase in CVC AUC0-24, and a 4.17-fold increase in Cmin with DRV/r co-administration, which is comparable to the effect seen with co-administration of RTV alone in Study 104. In Study 113, there was no meaningful effect of CVC on plasma darunavir (DRV) or RTV exposure.

In Study 108, there was a 2.55-fold increase in CVC Cmax, a 3.89-fold increase in AUC0-24, and a 5.75-fold increase in Cmin with ATV/r co-administration, which is comparable to the effect seen with co-administration of RTV alone in Study 104. In Study 112, there were modest effects of CVC on RTV Cmin (1.50-fold increase) and on atazanavir (ATV) Cmax (1.19-fold increase), AUC0-24 (1.33-fold increase), and Cmin (1.55-fold increase). There were no statistically significant effects of CVC on RTV Cmax or AUC0-24.

In Study 109, there was a 23% reduction in CVC Cmax, a 43% reduction in AUC0-24, and a 48% reduction in Cmin with EFV co-administration. CVC did not result in a meaningful change in plasma EFV exposure.

In Study 110, there was a 28% reduction in CVC Cmax, a 29% reduction in AUC0-24, and a 23% reduction in Cmin with DTG co-administration. CVC did not result in a meaningful change in plasma DTG exposure.

A summary of detailed results of these studies performed is shown in [Appendix I](#).

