In CENTAUR, the CVC dose of 150 mg daily exposed >77% of participants to minimum plasma concentration (C_{min}) values that exceed the EC_{min50} (C_{min} associated with half-maximal response; using most conservative EC_{min50} of 50 ng/mL, based on data from the HIV Phase II program), providing an expectation of substantial and near maximal antagonism of CCR2/CCR5 in most participants at this dose. When using the EC_{min50} of 40 ng/mL, which was based on changes in CCL2 and CCL4 levels (i.e., reciprocal increases in CCL2 and CCL4 levels observed due to effective CCR2 and CCR5 blockade by CVC) observed in the CENTAUR study, >84% of CVC-treated participants achieved this target drug concentration. Results from a drug interaction study (Study 652-123) have shown that administration of a proton pump inhibitor (PPI) 90 minutes prior to CVC, dosed at 150 mg, resulted in significantly decreased CVC concentrations. In the CENTAUR study, PPIs were allowed with specific dosing instructions (i.e., dosing of PPIs at least 2 hours after CVC 150 mg daily dose) and were used in 44% of all participants. Although fewer participants achieved an EC_{min50} of 40 ng/mL when using PPIs (84.5%) compared to those who did not (94.3%), a similar proportion of participants in both groups achieved the key efficacy endpoint of improvement in fibrosis by at least 1 stage and no worsening of steatohepatitis: 21.0% for PPI users versus 25.0% for nonusers, respectively (mITT). Therefore, the dose of 150 mg appears sufficient when managing coadministration of CVC with commonly used concomitant medications, such as PPIs. Taken together, prior PK/PD analyses further support that the CVC 150 mg dose was able to maximize CCR2/CCR5 blockade in most participants and support its evaluation in the current study.

This is also supported by data from the Phase 3, two-part AURORA study (3152-301-002), which aimed to confirm the antifibrotic benefit of CVC as compared with placebo in adults with NASH and Stage 2 or 3 fibrosis. Part 1 of the study was designed to demonstrate the superiority of CVC compared with placebo on liver histology at Month 12, relative to the screening biopsy in adult participants with a liver biopsy diagnosis of

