5.4.3 Precautionary Medications

Table 5.4.3-1: Precautionary Medications

Medicinal Product Class	Drugs that are Allowed but Must be Taken with Precaution During Intake of CVC (Mechanism)
Acid-reducing agents (H2 receptor antagonists, antacids, and PPIs)	
When required, acid-reducing agents should be administered at least 2 hours after the CVC dose to ensure that adequate CVC concentrations are maintained. When possible, use of an H2 receptor antagonist (except cimetidine) or antacids is preferred over a PPI. It is recommended to start with the lowest dose of these agents and titrate according to clinical response.
 
 H2 receptor antagonists (e.g., famotidine or ranitidine) should preferably be given from 2 to 12 hours after administration of CVC at a dose that does not exceed doses comparable to famotidine 40 mg daily. Antacids (e.g., aluminum hydroxide, calcium carbonate, magnesium carbonate, magnesium hydroxide, or bismuth subsalicylate) should preferably be given at least 4 hours after administration of CVC due to their immediate effect in increasing gastric pH. PPIs (e.g., omeprazole, lansoprazole, esomeprazole, pantoprazole, rabeprazole, or dexlansoprazole) should preferably be given approximately 3 hours after administration of CVC at a dose that does not exceed doses comparable to omeprazole 20 mg daily. Due to the prolonged acid-reducing effect of PPIs (~16 to 24 hours), it is advised to follow these dosing recommendations to reduce their potential impact on CVC absorption at subsequent dosing.
Lipid-lowering agents	Refer to Table 5.4.2-1 for the statin doses that are not allowed. Contact the A5415 CMC ([contact]) for any question regarding statin doses.

Medicinal Product Class	Drugs that are Allowed but Must be Taken with Precaution During Intake of CVC (Mechanism)
PDE5 enzyme inhibitors	
sildenafil, tadalafil, vardenafil (CYP3A4 substrates)
 
The recommended starting doses for these medications are as follows:
 
– sildenafil 25 mg– tadalafil 2.5 mg– vardenafil 2.5 mg

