11.2 Pharmacology Study Design

Participants will be enrolled who are stabilized on an NNRTI-based or unboosted INSTI-based ART regimen for ≥ 48 weeks prior to study entry. PK data available to date is specified in [section 2.1](#) (“Supporting Pharmacokinetic Data from Allergan/AbbVie”). Appropriate dosage adjustments will be made for participants on EFV-based ART based on these prior data. Data for those on INSTI-based ART is limited to DTG where modest reduction in CVC exposure (28% and 29% reduction in CVC Cmax and AUC 0-24 hr, respectively) was detected. Therefore, to provide information for CVC PK in individuals living with HIV on these regimens and to provide ART PK in the context of CVC specifically in individuals living with HIV, a sparse PK design will be completed. Since CVC should be taken with meals, information about whether or not dosing is done with food will be collected.

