11.3.2 Data Analysis

Pharmacokinetics

CVC Exposure: An average steady-state CVC trough concentration will be estimated by ART regimen (INSTI- or NNRTI-based ART) and compared between ART regimens and with historical data for CVC.

ART exposure: An average steady-state ART trough concentration will be estimated pre- and post-CVC/placebo for CVC dosing. Average steady state ART trough concentrations during CVC/placebo for CVC co-administration will be compared a) between those on CVC and those on placebo for CVC (inter-participant comparison) and b) with pre-CVC levels (intra-participant comparison).

Analyses will use time-adjusted linear mixed effect models with measured concentration log-transformed.

Pharmacodynamics

Correlation of CVC exposure to outcomes: A composite time-adjusted CVC exposure estimate over the 24-week study period will be obtained for each participant from the mixed effect modelling based on their measured concentrations at weeks 4, 8, 12, and 24. Associations of these empirical Bayes estimates and the following arterial inflammation outcomes measured will be estimated via Spearman's rank-based correlation.

- Change in most diseased vessel TBR from baseline to week 24
- Change in aortic TBR from baseline to week 24
- Change in carotid artery TBR from baseline to week 24
- Week 24 aortic TBR
- Week 24 carotid artery TBR

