9.1.1 Descriptive Statistics of CVC Trough Estimates by ART Class

Analysis set(s): Complete case set (cenicriviroc arm only)
Grouped by: a) ART Class (INSTI, NNRTI, both); b) ART Agent

Table	CVC Trough Estimates by ART Class / Agent
Characteristic	Summary Statistic(s)
Participant-level average CVC trough concentration	Median (Q1, Q3), and P10, P90
CVC trough concentration by week	Median (Q1, Q3), and P10, P90

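### The exploratory comparison of CVC troughs across non-randomised ART regimens does not account for acid-reducer use, which the protocol's own data link to lower CVC exposure

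*Protocol*

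**What the plan says.** **Evidence that exposure depends on acid reducers and food.** Protocol 2.1 (Rationale for 150 mg Dose) reports an interaction study in which a PPI taken 90 minutes before CVC "resulted in significantly decreased CVC concentrations". In CENTAUR, PPIs had to be taken at least 2 hours after CVC and "were used in 44% of all participants". Even so, attainment of 40 ng/mL was lower "when using PPIs (84.5%) compared to those who did not (94.3", both in percent). Appendix I (Study 652-1-111) reports that the DP7 tablet is absorbed better fed than fasting, particularly at 150 mg.

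**What this trial allows and records.** Protocol 5.4.3 permits acid reducers with precautions: "When required, acid-reducing agents should be administered at least 2 hours after the CVC dose to ensure that adequate CVC concentrations are maintained". Medication history carries start and stop dates (6.3.3). New and discontinued prescription and non-prescription drugs are recorded after entry (6.3.4). On food, 11.2 says that "information about whether or not dosing is done with food will be collected".

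**What the analysis uses.** Protocol 11.3.2 compares average CVC trough between ART regimens and describes the model in one sentence: "Analyses will use time-adjusted linear mixed effect models with measured concentration log-transformed". Section 11.3.1 restricts samples by missed doses and time since dose only. SAP 9.1.1 lists "Participant-level average CVC trough concentration" and trough by week, as medians and percentiles by ART class or agent. No section brings acid reducers or food into the CVC trough comparison.

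**The concern.** Participants enter on the regimen they already take, so randomisation to CVC or placebo does nothing to balance acid-reducer use between, for example, bictegravir, dolutegravir and rilpivirine users within the CVC arm. A regimen group with more PPI users would tend to show lower CVC troughs even if the antiretroviral had no effect. With the opposite imbalance, a real interaction could be hidden. The problem remains when dose and time after dose are equal.

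At stake is the reading of objective 1.4.7a and of the first pharmacology objective in protocol 11.1. A table of troughs by agent is likely to be read as interaction evidence, and protocol 2.1 gives CVC pharmacokinetics on selected regimens as one reason for the sparse PK design.

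**Working it through.** **Inputs from the documents**
- Attainment of 40 ng/mL in CENTAUR: 84.5% with PPI, 94.3% without; PPI use 44% (protocol 2.1).
- Overall attainment: ">84% of CVC-treated participants achieved this target drug concentration" (protocol 2.1).
- Yardstick: 23% lower CVC Cmin with dolutegravir (protocol 2.1, Study 110).
- CENTAUR CVC group in the Year 1 safety set: 144 (Table 2.1-2).
- SAP section 9 considers only agents with at least 10 exposed participants.

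**Assumptions, not in the documents**
- Troughs log-normal with the same log-SD in PPI users and non-users; log-SD 0.4 to 0.9.
- Difference in PPI use between two regimens: 10, 20 or 40 percentage points.

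**Step 1: consistency.** No counts are given behind 84.5% and 94.3%, so the pair cannot be rebuilt. The weighted mean is 0.44 × 84.5 + 0.56 × 94.3 = 90.0%. That satisfies the stated lower bound of 84%, although the figures may come from different sets.

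**Step 2: implied shift.** With a common threshold and equal SD, the shift in log-SD units is z(0.943) − z(0.845) = 1.580 − 1.015 = 0.565.

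**Step 3: trough ratio, PPI to no PPI**, exp(−0.565 × log-SD):
- log-SD 0.4: 0.80, about 20% lower.
- log-SD 0.9: 0.60, about 40% lower.

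**Step 4: spurious regimen ratio with no true ART effect**, exp(−0.565 × log-SD × difference in PPI share):

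| PPI imbalance | log-SD 0.4 | log-SD 0.9 |
|---|---|---|
| 10 points | 2.2% lower | 5.0% lower |
| 20 points | 4.4% lower | 9.7% lower |
| 40 points | 8.6% lower | 18.4% lower |

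On the log scale the dolutegravir effect is −ln(0.77) = 0.261. The 20- to 40-point rows amount to between (0.565 × 0.4 × 0.2)/0.261 = 0.17 and (0.565 × 0.9 × 0.4)/0.261 = 0.78 of it.

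**Step 5: could such an imbalance arise?** Suppose both regimens share the same true PPI use, between 20% and 44%. Exact binomial calculation then gives a chance of an observed difference of 20 points or more of 21% to 32% for assumed groups of 10 and 30, and of 9% to 17% for groups of 20 and 40. The group sizes are illustrative.

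**Step 6: uncertainty of the CENTAUR pair.** If the percentages came from 144 participants split 44/56, that is about 63 and 81, the standard error of the 9.8-point gap is √(0.845 × 0.155/63 + 0.943 × 0.057/81) = 0.052. The 95% interval is about −0.5 to 20 points. The 0.565 shift then has an interval of about 0 to 1.1 log-SD.

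**The case against.** **No planned inference is shown to be biased.** The objective is exploratory. SAP 9.1.1 is headed as descriptive and contains no test or contrast. SAP section 9 declares itself subject to change, and a separate implementation plan will follow. This stands and limits the priority of the point. Protocol 11.3.2 does still commit to a comparison between regimens, and the SAP's openness to change means the gap can be closed now.

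**Naming time does not exclude other covariates.** This is fair: the model gets one sentence. But neither document names another covariate, and the SAP display has none.

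**The design already limits both factors.** CVC is taken with food. Acid reducers are separated from it, H2 blockers and antacids are preferred, and PPI dose is capped. Protocol 2.1 describes only the 2-hour separation for CENTAUR, so carrying its contrast over may overstate the effect here. That stands. The figures also concern PPIs only; for H2 blockers and antacids there is only dose and timing advice.

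**The adjustment would be imperfect.** Section 6.3.10 records dates and times of CVC and ART doses, not of acid reducers. Section 11.2 does not say that food is captured for the doses before PK visits. Both points stand and shape the fix.

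**Stronger readings the documents do not support.** A reader might infer that the regimen comparison is in fact distorted. With no PPI use by regimen, that cannot be said. A reader might also think protocol 2.1 treats PPIs as harmless to exposure because fibrosis response was similar (21.0% and 25.0%). It states the lower attainment openly and uses fibrosis response to argue that the dose is sufficient, so the later failure of AURORA on histology has no bearing here. Nor is the regimen contrast the sole purpose of the PK work: ART exposure under CVC and the exposure–outcome association are purposes too.

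**Conclusion.** The point holds as a modest, inexpensive improvement to an exploratory analysis. The protocol documents lower CVC exposure with PPIs and better absorption with food, then compares troughs across non-randomised regimens without using either factor.

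The possible distortion is about 4% to 18% of the trough ratio for a 20- to 40-point imbalance in PPI use, and about 5% or less for 10 points. These figures rest on log-normal troughs, an assumed log-SD of 0.4 to 0.9, an assumed imbalance, and a non-randomised CENTAUR contrast that is imprecise under the sample split assumed above. The interaction study supports the direction of the PPI effect but gives no size. The actual size and direction in this trial are unknown. For food, the documents give a direction of effect but no reason to expect a difference between regimens. The primary, secondary and safety analyses are unaffected.

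**What to change.** In protocol 11.3.2 and SAP 9.1.1:

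1. Keep the crude medians as description, and tabulate acid-reducer use (any, and PPI) by ART class and agent beside them.
2. Estimate the regimen contrasts from the log-concentration mixed model with ART agent, time since dose and acid-reducer use at the visit (yes/no, derived from recorded start and stop dates). Enter PPI use separately if numbers allow.
3. Add food with the last CVC dose as a covariate only if it is captured for the doses preceding the PK samples; otherwise say that it is not.
4. Report one sensitivity run without PPI users.

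The cost is SAP wording, one or two degrees of freedom, and wider intervals in small regimen groups. The acid-reducer term uses medication data already planned. Some residual confounding will remain, because the timing of acid reducers relative to CVC is not shown to be recorded; the report should say so.
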